11.0 ADVERSE AND SERIOUS ADVERSE EVENTS

11.1 GENERAL DEFINITIONS

An Adverse Event (AE) is any untoward medical occurrence in a patient or a clinical trial subject which does not necessarily have a causal relationship with the device/procedure.

A Serious Adverse Event (SAE) is an untoward occurrence that:

- Is fatal
- Is life threatening
- Requires hospitalisation or prolongation of existing hospitalisation
- Results in persistent or significant disability
- Consists of a congenital anomaly or birth defect
- Is otherwise considered medically significant by the Investigator

Medical and scientific judgement must be exercised in deciding whether an event is serious. There characteristics/consequences must be considered at the time of the event and do not refer to an event which hypothetically may have caused one of the above. All potential intervention-related AEs (such as falls and consequent injuries related to wearing the insoles) will be investigated and subject to expedited reporting to the REC.

12.0 OPERATIONAL DEFINITIONS OF (S)AES

12.0.1 Expected (S)AEs - Not Reportable

This is a trial in a patient population with high levels of morbidity and co-morbid diseases and as such in this patient population, acute illness resulting in hospitalisation, new medical problems and deterioration of existing medical problems are expected.

In recognition of this, events fulfilling the definition of an adverse event or serious adverse events will not be reported in this study unless they are classified as 'related'.

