8.2 EXCLUSION CRITERIA

- Either foot has less than 2 arterial vessel run-off on Doppler.
- Poor visual acuity ie registered blind, unless supported by carer.
- Current participation in another clinical investigation of a medical device or a drug; or participation in such a study within 30 days prior to study enrolment.
- Body Mass Index (BMI) >40.
- Participant has bespoke contact insoles and footwear.
- Participant is unable to use 'medium' or 'large' insoles due to foot size eg. small or extra large feet.
- Participant has a pacemaker.
- Participant is pregnant.

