12.0.2 Expected (S)AEs - Standard Reporting

The following AEs and SAEs are expected within the patient study population and will be reported from randomization to trial completion on standard Case Report Forms (CRFs) where the device is not a factor in the event:

- Death
- Hospital admission

- Institutionalisation

As these events are expected within the study population they will not be subject to expedited reporting to the main REC.

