12.2 RESPONSIBILITIES

Community Foot Protection Team:

- Checking for SAEs when participants attend following an alert from Path Active or there is concern from either Path Active Group or Control Group participants
- Judgement in assigning:
 - Seriousness
 - Relatedness
 - Expectedness
- To ensure all SAEs are recorded and reported to the CI within 24 hours of becoming aware and to provide further follow-up information as soon as available.

CI or delegate:

- Assign relatedness and expected nature of SAEs where it has not been possible to obtain local assessment.
- Undertake SAE review.
- Review all events assessed as Related / Unexpected in the opinion of the CI prior to reporting to the main REC.

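### Section 12.0.1 bars reporting of any AE or SAE not classed as related, which contradicts sections 12.0.2 and 12.2

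*Protocol*

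**What the plan says.** Three sections of the protocol govern what sites do with an adverse event that is not attributed to the device.

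- **Section 12.0.1** notes that the population is ill, lists hospitalisation for acute illness and new medical problems as expected, and concludes that "events fulfilling the definition of an adverse event or serious adverse events will not be reported in this study unless they are classified as" related. It states no exception.
- **Section 12.0.2** names death, hospital admission and institutionalisation. It says these "will be reported from randomization to trial completion on standard Case Report Forms (CRFs) where the device is not a factor in the event". It then exempts them, in a separate sentence, from expedited reporting to the main REC.
- **Section 12.2** makes the Community Foot Protection Team responsible as follows: "To ensure all SAEs are recorded and reported to the CI within 24 hours of becoming aware". No relatedness condition is attached. The CI or delegate is to "Assign relatedness and expected nature of SAEs where it has not been possible to obtain local assessment".

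Section 11.1 defines an AE by reference to the device/procedure and lists six criteria for seriousness, the last being "Is otherwise considered medically significant by the Investigator". Section 10.2 schedules an adverse events review at visit 3 (alert or concern) and at visit 4 (Day 84).

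**The concern.** A site cannot follow 12.0.1 and also follow 12.0.2 and 12.2. Four sites will work from this text. One that takes 12.0.1 literally will hold fewer SAE records than one that takes 12.2 literally, and events never written down may not be recoverable later. Rules on safety recording belong in the protocol, so a separate analysis plan would not settle the matter.

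A second, conditional worry follows from the form of the rule. Relatedness refers to the device/procedure, and only one arm has the device. A filter based on relatedness therefore cannot work in the same way in both arms. That matters if new foot ulcers reach the database as adverse events, because section 6.0 asks whether the device is as effective as routine podiatry in preventing them.

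**Working it through.** The protocol gives no figure on this point, so the check sets the sections side by side.

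**Step 1. An unrelated death, hospital admission or institutionalisation.**

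| Section | Instruction |
|---|---|
| 12.0.1 | not reported |
| 12.0.2 | reported on a CRF |
| 12.2 | if an SAE, recorded and sent to the CI within 24 hours |

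Sections 12.0.2 and 12.2 can be followed together. Section 12.0.1 opposes both.

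**Step 2. Treat 12.0.2 as an exception to 12.0.1.** Section 11.1 has 6 seriousness criteria. The 12.0.2 list covers 2 of them (fatal; hospitalisation). One more, congenital anomaly, is nearly empty, because section 8.2 excludes anyone meeting "Participant is pregnant". That leaves 6 − 2 − 1 = 3: life threatening, persistent or significant disability, and medically significant. An unrelated event that is serious on one of these grounds alone is still barred by 12.0.1 and still required by 12.2. Some disabling events may also lead to institutionalisation and so fall under 12.0.2, but not all need do so.

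**Step 3. Treat 12.0.1 as a limit on REC reporting only.** This would remove the conflict, but it is not what the section says. It speaks of reporting in the study, whereas 12.0.2 names the REC when it means the REC.

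**Step 4. A new, non-serious foot ulcer in a control participant.** Section 8.1 requires both feet to be free of ulceration at entry, so an ulcer during follow-up is a new untoward occurrence and meets the AE definition.

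- 12.0.1: barred unless related. Controls have no device, so this could be met only through a study procedure.
- 12.0.2: not listed, unless the ulcer leads to admission or institutionalisation.
- 12.2: outside its scope, which is SAEs, unless the ulcer is judged medically significant or meets another seriousness criterion.
- 15.1.2: the only endpoint that mentions ulceration reviews Path Active alerts, which controls do not have.

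No reporting route is therefore stated for such an ulcer, provided that 12.0.1 is applied as written and ulcers are captured through AE reporting.

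**Step 5. Scale, by assumption only.** The protocol gives no ulcer rate for high-risk people with intact feet. Assume 60 controls (120 ÷ 2, with 1:1 allocation assumed), a constant hazard and an annual risk *a*. The 84-day risk is then 1 − (1 − *a*)^(84/365.25).

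| Assumed annual risk | 84-day risk | Controls with an ulcer, of 60 |
|---|---|---|
| 5% | 1.2% | 0.7 |
| 10% | 2.4% | 1.4 |
| 20% | 5.0% | 3.0 |
| 40% | 11.1% | 6.6 |

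The 40% row borrows the first-year recurrence figure in section 5.1, which describes people who have already had an ulcer. These counts cover ulcers of any seriousness. They show only that few events would be expected, so that losing a handful would matter. They do not estimate how many would be lost.

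**The case against.** The strongest reply is that 12.0.1 and 12.0.2 stand under parallel headings, as tiers of expected events, and that a specific list after a general rule is naturally read as an exception. Moreover, someone must receive an SAE before relatedness can be assigned, and 12.2 provides for that, so 12.0.1 may be meant as a filter on onward reporting. Both readings are reasonable guesses at intent, but the text states neither. The first still leaves the three criteria in step 2 in conflict.

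On ulcers the reply has more force. Nothing says that ulcers are counted from AE reports. Forms F07, F08 and F09 are not shown. Visit 3 includes eligibility confirmation, and eligibility includes intact feet. It also includes medical history. Section 12.2 extends visits for concern to controls, who continue regular podiatry, and section 16.0 provides for access to medical records. None of this states an ulcer record, but it means that the ulcer point can only be conditional.

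A reader might infer three stronger things that the protocol does not support.

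- **That ulcer counts will be biased against the device.** An ulcer that the device merely failed to prevent need not be judged related, so it may be filtered out just as a control ulcer would be. No between-arm safety analysis or between-arm ulcer endpoint is specified.
- **That the lack of a neuropathy test or Doppler at week 12 proves that ulcers go unseen.** Neither is an inspection for ulcers.
- **That 11.1 and 12.2 conflict over the REC.** Section 11.1 says potential intervention-related AEs "will be investigated and subject to expedited reporting to the REC". Section 12.2 has the CI "Review all events assessed as Related / Unexpected in the opinion of the CI prior to reporting to the main REC". One says what is expedited and the other says what is reviewed beforehand, so they can coexist.

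**Conclusion.** The contradiction stands and should be fixed. It lies in the current text and rests on no assumption: for an unrelated death, admission or institutionalisation, 12.0.1 says the opposite of 12.0.2 and 12.2. On the most favourable reading that the wording allows, 3 of the 6 seriousness criteria remain in conflict between 12.0.1 and 12.2.

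The ulcer consequence is conditional on two things: that sites apply 12.0.1 literally, and that new non-serious ulcers are captured through AE reporting. If both hold, control-arm ulcers have no stated reporting route in a trial that asks about ulcer prevention. It is not shown that ulcers will go unrecorded, nor how many, nor in which direction a comparison would move.

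**What to change.** Reconcile 12.0.1, 12.0.2 and 12.2 into one rule that treats recording (CRF entry and notice to the CI) separately from onward reporting to the REC.

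- Record all SAEs and all new foot ulcers in both arms, from randomisation to Day 84, regardless of relatedness.
- Use the AE reviews already scheduled at visits 3 and 4, and say so in section 10.2. Visit 3 happens only on an alert or concern, so an ulcer that prompts neither would first be captured at visit 4. The Day 84 review should therefore ask about new ulcers since randomisation.
- Let relatedness and expectedness limit only what goes on to the REC.

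If the existing forms already record ulcers in both arms, a sentence naming the form settles that part. The cost is protocol wording and some extra CRF entries in a population with high morbidity. The number of entries cannot be estimated from the protocol. No visit is added.

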12.0.2 Expected (S)AEs - Standard Reporting

The following AEs and SAEs are expected within the patient study population and will be reported from randomization to trial completion on standard Case Report Forms (CRFs) where the device is not a factor in the event:

- Death
- Hospital admission

- Institutionalisation

As these events are expected within the study population they will not be subject to expedited reporting to the main REC.

12.2 RESPONSIBILITIES

Community Foot Protection Team:

- Checking for SAEs when participants attend following an alert from Path Active or there is concern from either Path Active Group or Control Group participants
- Judgement in assigning:
 - Seriousness
 - Relatedness
 - Expectedness
- To ensure all SAEs are recorded and reported to the CI within 24 hours of becoming aware and to provide further follow-up information as soon as available.

CI or delegate:

- Assign relatedness and expected nature of SAEs where it has not been possible to obtain local assessment.
- Undertake SAE review.
- Review all events assessed as Related / Unexpected in the opinion of the CI prior to reporting to the main REC.

13.0 DATA MANAGEMENT AND QUALITY ASSURANCE

13.1 CONFIDENTIALITY

The study will abide by the Caldicott Principles, the Data Protection Act 2018 and General Data Protection Regulations for reviewing and managing personal data. All data will be kept confidential, stored appropriately and anonymised in as far as is possible. As with standard clinical practice, confidentiality may need to be broken if participants or others are at serious risk. This will be explained to participants when they consent to participate in the project.

All participants will be given a study number, allocated sequentially by the clinical team. The study will comply with the General Data Protection Regulation (GDPR) which requires data to be anonymised as soon as it is practical to do so. Data will be analysed anonymously.

The CRF will not bear the subject's name or other directly identifiable data. The subject's trial Identification Number (ID) only, will be used for identification. Participant identifiable information (e.g. the signed consent form) will be kept with the study number securely by local study teams, in case of

the unlikely requirement for breaking confidentiality. This list matching identifiable participant information and study numbers will not be kept outside of the local study team.

13.2 DATA COLLECTION

Data Collection will be via a paper CRF completed by the study team. Any data eg spreadsheet of participants, will be processed via NHS IT systems and stored in secure network folders.

13.3 DATA HANDLING AND ANALYSIS

CRFs will be completed on paper. Data collected will be stored on secure server and in excel files.

Study documents (paper and electronic) containing details of demographic data, documentation of inclusion and exclusion criteria, and medical history will be retained for a period of 5 years following the end of the study

13.4 TRANSFERRING/TRANSPORTING DATA

If data transfer is required, it will only be transferred via secure nhs.net email and will be anonymised.

14.0 ARCHIVING

During the course of research, all central records are the responsibility of the Principle Investigators and must be kept in secure conditions. The PIs will have responsibility for storage of consent forms and a list of patient identifiers with study numbers. The PIs will archive the trial essential documents generated at the site for the agreed archiving period in accordance with the signed Clinical Trial Site agreement.

The trial essential documents along with the trial database will be archived in accordance with the sponsor. The agreed archiving period for this trial will be 5 years.

15.0 ENDPOINT DESIGN

15.1 ENDPOINTS

15.1.1 PRIMARY ENDPOINTS

- Day 84 all participants will be asked to complete a health-related quality of life questionnaire and a questionnaire regarding patient experience and, for the Path Active Group, use of the device and suggested improvements with the device and associated 'app'.
- To model any reduction in carbon footprint due to ulcer prevention.

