3.0 STUDY SUMMARY

Official title:	Path Active; A multicentre randomised controlled trial
Brief title /Acronym:	PAM RCT
Sponsor reference number:	WWPP2.002
Public database trial ID:	TBC
Research Question	To evaluate the effectiveness of Path Active™ in people with diabetes who are at 'high risk' of foot ulceration.
Study design	Multicentre effectiveness randomised controlled trial
Eligibility criteria:	
Inclusion criteria:
 
 - Participant able to give informed consent. - Age >18 at the time of consent. - Diagnosis of Type 1 or Type 2 Diabetes. - Both Feet Intact (no ulceration). - Participant understands and is willing to participate and can comply with the follow-up regime. - Participant diabetes foot Risk Stratification as 'High Risk'. - Ability to walk independently for > 100 metres i.e without use of wheelchair, walking stick or personal assistance. - Participant able and willing to wear suitable footwear. - Must own a mobile phone and be willing to upload WWP app. 
Exclusion Criteria:
 
 - Either foot has less than 2 arterial vessel run-off on Doppler. - Poor visual acuity ie registered blind, unless supported by carer. - Current participation in another clinical investigation of a medical device or a drug; or participation in such a study within 30 days prior to study enrolment. - Body Mass Index (BMI) >40. - Active osteomyelitis (bone infection) suspected or diagnosed. - Active Charcot's neuroarthropathy. - Participant has bespoke contact insoles and footwear. - Participant is unable to use 'medium' or 'large' insoles due to foot size eg. small or extra large feet. - Participant has a pacemaker.

	- Participant is pregnant.
Anticipated start date	2 nd April 2024
Anticipated end date	31 st March 2025
Target number of participants	120
Primary aim(s)	The primary objective of this clinical investigation is to evaluate the effectiveness of Path Active™ in people with diabetes who are at 'high risk' of foot ulceration.
Secondary aim(s)	To establish the 'carbon footprint' of Path Active in different geographies.
Sources of funding	SBRI Healthcare Selection Panel. Ref SBRIH22P2006
Sponsor	Walk With Path

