6.0 RESEARCH QUESTIONS

- Is Path Active as effective as regular routine podiatry review in foot ulcer prevention?
- Does using Path Active improve participant QoL?
- Are there any suggestions from participants to improve the device/app?
- Will preventing foot ulceration reduce NHSE carbon footprint?

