6.1 PRIMARY AIM

The primary objective of this clinical investigation is to evaluate the effectiveness of Path Active™ in people with diabetes who are at 'high risk' of foot ulceration compared to regular routine podiatry clinical review.

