15.1.2 SECONDARY ENDPOINTS

- At end of study review all alerts from Path Active and responses to the alerts. Was ulceration prevented? Were there any conflicting outcomes from device use?

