15.2 ANALYSIS PLANS

15.2.1 PRIMARY ENDPOINT ANALYSIS

Day 84; Data will be analysed to determine the effectiveness of 'Path Active' compared with standard podiatry review.

Questionnaires will be reviewed for QoL outcomes and patient experience.

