15.2.2 SECONDARY ENDPOINT ANALYSIS

Day 84; Alerts from Path Active will be analysed to assess a base level of sensitivity and specificity.

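### The first research question is ulcer prevention against routine podiatry, but no between-arm ulcer endpoint is defined and no foot check is listed at Day 84

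*Protocol*

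**What the plan says.** Section 6.0 opens with the question "Is Path Active as effective as regular routine podiatry review in foot ulcer prevention". Section 6.1 sets the primary aim as effectiveness in people at high risk of "foot ulceration compared to regular routine podiatry clinical review", without naming an outcome variable. Section 15.2.1 promises, for Day 84, that "Data will be analysed to determine the effectiveness of 'Path Active' compared with standard podiatry review", again without a variable.

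The primary endpoints in Section 15.1.1 are of two kinds. The first is questionnaires: "Day 84 all participants will be asked to complete a health-related quality of life questionnaire and a questionnaire regarding patient experience", with device feedback added in the Path Active Group. The second is "To model any reduction in carbon footprint due to ulcer prevention". Elsewhere carbon is secondary: the Section 3.0 summary gives as its secondary aim "To establish the 'carbon footprint' of Path Active in different geographies", and Section 6.2 also lists carbon modelling under secondary aims.

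The secondary endpoint in Section 15.1.2 reads "At end of study review all alerts from Path Active and responses to the alerts. Was ulceration prevented", and its analysis in Section 15.2.2 is that "Alerts from Path Active will be analysed to assess a base level of sensitivity and specificity".

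**The concern.** A randomised trial answers a question about ulcer prevention by counting ulcers in the same way in both arms. Here the variable that the first question needs is not among the primary endpoints. As a secondary matter it appears only inside a review of alerts, which exist in one arm. If no one examines feet at Day 84, an analysis plan written later cannot recover the missing observation.

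Three things depend on that variable: the effectiveness comparison promised in Section 15.2.1, the carbon model (whose input is the number of ulcers prevented), and the alert accuracy analysis (which needs to know who ulcerated, including those who never had an alert). The quality-of-life and device-feedback questions do not depend on it.

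**Working it through.** **Step 1. Research questions against endpoints.**

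| Question (Section 6.0) | Where it is addressed |
|---|---|
| Ulcer prevention versus podiatry | No between-arm endpoint; raised in 15.1.2 within the alert review, device arm only |
| Quality of life | 15.1.1, Day 84 questionnaire, both arms |
| Suggestions for device and app | 15.1.1, Day 84 questionnaire |
| Carbon footprint | 15.1.1, a model that takes ulcer prevention as its cause |

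**Step 2. Where ulcer status could be learned.**

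- *Screening.* Section 8.1 requires both feet to be free of ulcers, and Section 10.2 ticks eligibility confirmation. Baseline status is therefore known.
- *Alert or concern visit (visit 3).* Section 10.2 ticks eligibility confirmation again. Read with Section 8.1, this implies that ulcer status is rechecked there. Section 12.2 opens concern visits to both arms; alerts arise only in the device arm.
- *Day 84.* Section 7.1 lists EQ-5D-5L, the patient questionnaire and, for device users, return of the device. The final-visit column of Section 10.2 has the two questionnaires and an adverse event review. Neither place lists a foot item. The neuropathy assessment is at screening only, and the Doppler assessment at screening and visit 3.
- *Adverse events.* A new ulcer meets the Section 11.1 definition. Section 12.0.1 then leaves out events not classed as related, and Section 12.0.2 brings back only death, hospital admission and institutionalisation. Section 12.2 asks for every serious event to be recorded and sent to the Chief Investigator, which does not fit Section 12.0.1. A non-serious ulcer not classed as related has no clear route; a serious one falls under statements that disagree.

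So ulcer status is not systematically known for a participant with neither an alert nor a concern visit. The sensitivity and specificity analysis lacks a reference status for those same participants.

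**Step 3. Comparability of the arms.** Daily dashboard review and alert-triggered visits exist only in the device arm (Sections 7.1 and 10.2). The chance that an ulcer is noticed can therefore depend on allocation.

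**Step 4. Size, as illustration only.** The stated total of 120 (Section 7.1) cannot be reproduced, because the event rates, the effect and the power are not given. The inputs below are the 40% first-year recurrence rate (Section 5.1), 84 days of follow-up, and 120 completers. Assumed: constant hazard, 1:1 allocation (60 per arm), two-sided 5% level.

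- Risk by Day 84: 1 − 0.6^(84/365) = 0.1109. Expected ulcers per arm: 60 × 0.1109 = 6.65.
- Half-width of the 95% CI for the risk difference at equal risk: 1.96 × √(2 × 0.1109 × 0.8891 / 60) = 0.112, about 11 points.
- Power for a halving (0.1109 versus 0.0555, pooled-variance formula). Mean risk 0.0832; standard error under the null √(2 × 0.0832 × 0.9168 / 60) = 0.0504; under the alternative √((0.1109 × 0.8891 + 0.0555 × 0.9445) / 60) = 0.0502. Then Φ((0.0555 − 1.96 × 0.0504) / 0.0502) = 0.19. Reaching 80% takes 389 per arm, 778 in total.
- At an assumed 20% per year: 1 − 0.8^(84/365) = 0.0501, 3.0 ulcers per arm, half-width 0.078, power for a halving 0.107.
- Each ulcer missed in one arm moves the risk difference by 1/60 = 1.7 points. Two missed move it by 3.3 points, against an expected 6.65 ulcers in that arm (2/6.65 = 30%).

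**The case against.** The strongest reply is that ulcers may well be recorded somewhere. The flow chart in Section 4.0 and the contents of the case report forms are not visible, and either could hold a Day 84 foot item. Section 5.1 describes clinic checks at least monthly for high-risk patients, so clinic records would show some ulcers. This limits the finding to the text shown. It does not remove it: the two visible Day 84 lists contain no foot check, and a form item would not supply the endpoint that Sections 15.1 and 15.2 leave out.

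Section 6.0 also does not rank its four questions, and the primary endpoints do serve the other three. That is fair, but Section 15.2.1 promises the comparison with podiatry under the primary analysis, and nothing else in the plan supplies its variable.

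A reader might infer more than the documents support:

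- *That no ulcer would be captured, or that the alert analysis has no reference status at all.* The eligibility tick at alert and concern visits speaks against this, and the adverse event sections are inconsistent rather than closed.
- *That device users lose routine podiatry, biasing the result in a known direction.* Section 7.1 states continued podiatry for controls but does not withdraw it from the device arm. The fewer clinic visits mentioned in Section 5.2 are rationale for the product, not a trial procedure.
- *That the wording of the first question contradicts a superiority sample size.* The reference list includes a binary superiority calculator, but Section 7.1 does not cite it, and a research question is not a formal hypothesis.
- *That the power figures prove the defect.* They apply a recurrence rate to a population not restricted to previous ulcers. The gap is structural and would exist at any event rate.

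**Conclusion.** The point holds as a structural gap and should be closed before participants reach Week 12. The protocol asks first about ulcer prevention against routine podiatry and promises that comparison. It defines no ulcer outcome compared between randomised arms and, in the text shown, schedules no foot check at Day 84. Ulcer status is implied only at screening and at alert or concern visits. Detection can therefore depend on allocation, by an amount and in a direction that the documents do not allow one to estimate.

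The figures serve only to show the scale: roughly 3 to 7 ulcers per arm across the two annual rates tried, a confidence interval of about ±8 to ±11 points, and 11% to 19% power for a halving. They rest on constant hazard, equal allocation and 60 completers per arm. With so few events, a couple of unrecorded ulcers in one arm would matter.

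**What to change.** - Define at least one new foot ulcer between randomisation and Day 84, compared between the randomised arms, as the primary effectiveness endpoint for the first research question. If the sponsor prefers to keep the Section 15.1.1 endpoints as primary, make it a named key secondary endpoint and reword the primary aim to match.
- Record it for every participant at the existing Week 12 visit, with the same brief foot check and the same form entry in both arms. Supplement it from clinic records since randomisation, noting the source of each ulcer. Because records and alert visits may differ by arm, also report ulcers present at the Week 12 check alone.
- Reconcile the status of the carbon endpoint between Sections 3.0 and 6.2 (secondary) and Section 15.1.1 (primary).
- Report the risk difference with its 95% confidence interval. Do not present 120 as powering this comparison unless the number is re-justified for it.

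The cost is a protocol amendment, a short check and one form entry at a visit that already takes place. Section 16.0 asks consent for record access in a monitoring context, so that wording may need checking before clinic records are used. No extra visit is needed. The ulcer estimate will stay imprecise at this sample size and should be presented as such.

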4.0 STUDY FLOW CHART

5.0 INTRODUCTION

5.1 BACKGROUND

More than 4.9M people have been diagnosed with diabetes (DM) in the UK, and up to 25% (1.2M) will develop a Diabetic Foot Ulcer (DFU) in their lifetimes. 15-20% of DFUs lead to amputations which are followed by significantly increased mortality. The cost to taxpayers is enormous (Kerr 2019), consuming 1% of NHS budget annually.

The current method of providing periodic foot checks is inadequate, with the chance of recurrence of an ulcer being 40% in the first year, rising to almost 100% over 10 years (Armstrong 2017). Individuals at high risk of DFU go to clinic to have their feet checked at least once a month. This can be highly disruptive to their everyday lives. Furthermore, there is considerable environmental cost of patient travel and if a DFU occurs single-use consumables for treatment such as dressings, bandages, scalpels, blood tests, cultures for microbiology , etc.

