6.2 SECONDARY AIMS

To model the carbon dioxide reduction that may occur if ulceration and the need for ulcer treatment is prevented, in differing UK geographies.

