7.0 TRIAL DESIGN

7.1 METHOD

Study setting

Participants who have been assessed as having a 'high risk' of foot ulceration will be recruited from Community Foot Protection Teams in 4 sites across the UK. Participants will be recruited to the study to a maximum total of 120 (30 at each site) who have completed the study. The number of recruits required is based on a power calculation for the study at the 95% confidence interval.

The study is anticipated to run for 12 months.

Procedure

Potential participants will be approached to participate during routine review by the Community Foot Protection Teams and consented by them for the study. All participants will be screened at pre-assessment by the Community Foot Protection Teams.

Following completion of informed consent the participant will have;

- Medical History
- Arterial Doppler scan

- Test for Neuropathy
- Eligibility confirmation
- EuroQoL Assessment (EQ-5D-5L)
- Patient Questionnaire
- Randomised to 'Path Active Group' or 'Control Group' using computer randomisation.

If the participant is randomised to use the device in the 'Path Active Group';

- Participant Training in device and mobile app use (Appendix 1).

If there is an alert from Path Active app the participant will be asked to reduce walking and rest their feet. If the alert continues and activates the clinical dashboard, patients will be contacted to attend clinic for review.

If the participant is not randomised to use the device in the 'Control Group', they will continue with their regular podiatry clinical reviews with the Community Foot Protection Team who will provide their standard of care.

Day 84 (week 12). At the end of study;

- EuroQoL Assessment (EQ-5D-5L)
- Patient Questionnaire

If the participant is randomised to use the device;

- Device retained by clinical research team.

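### The carbon objective is two different quantities at two ranks, and the primary carbon endpoint covers only avoided ulcer care, so it can neither give Path Active's footprint nor show a net increase

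*Protocol*

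**What the plan says.** Carbon appears in four places in the Protocol.

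- Study Summary (3.0), secondary aim: "To establish the 'carbon footprint' of Path Active in different geographies".
- Research Questions (6.0), unranked: "Will preventing foot ulceration reduce NHSE carbon footprint".
- Secondary Aims (6.2): "To model the carbon dioxide reduction that may occur if ulceration and the need for ulcer treatment is prevented, in differing UK geographies".
- Primary Endpoints (15.1.1): "To model any reduction in carbon footprint due to ulcer prevention".

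The primary endpoint analysis (15.2.1) does not mention carbon.

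Other sections describe activity that produces or saves emissions. The Background (5.1) says that "there is considerable environmental cost of patient travel" and adds single-use consumables when an ulcer occurs. The Rationale (5.2) describes sensor insoles, an app, a web portal and a clinical dashboard, and expects clinic visits to become less frequent. For the device arm, the Method (7.1) says: "If the alert continues and activates the clinical dashboard, patients will be contacted to attend clinic for review". It also says that the research team keeps the device at the end of the study.

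**The concern.** The footprint of a product and the emissions avoided through its benefit are different quantities, and one does not yield the other. The Study Summary asks for the first; 6.0, 6.2 and 15.1.1 ask for the second. A reader who takes the Study Summary as the aim will not find it answered by the listed endpoint.

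The rank is also inconsistent, because a secondary aim has become a primary endpoint. Both aims promise results by geography, and the endpoint does not.

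What is at stake is the environmental conclusion. An endpoint that counts only reductions through prevented ulcers can be reported as a carbon benefit of the device without the device's own emissions having been counted.

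**Working it through.** The Protocol states no carbon figure, so there is none to reproduce. The check compares the wordings and then writes out what the endpoint contains.

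**Side by side**

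| Place | Quantity | Rank | By geography |
|---|---|---|---|
| 3.0 | Footprint of Path Active | Secondary | Yes |
| 6.0 | Effect of preventing ulcers on the NHSE footprint | Unranked | No |
| 6.2 | Reduction if ulcers and their treatment are prevented | Secondary | Yes (UK) |
| 15.1.1 | Reduction due to ulcer prevention | Primary | No |

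Sections 6.0, 6.2 and 15.1.1 agree on the quantity, and 3.0 is the outlier. On rank, 3.0 and 6.2 agree and 15.1.1 is the outlier.

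**What the endpoint contains.** Per participant in the device arm, let:

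- k = ulcers prevented;
- U = emissions of one ulcer's care, including its own travel;
- D = device and app emissions;
- A = travel for alert-triggered visits;
- R = change in routine foot-clinic travel compared with control (negative if there are fewer visits).

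The endpoint as worded is S = k × U.

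The net saving is S − (D + A + R).

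**What follows**

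1. With no ulcers prevented, k = 0 and S = 0. The net change is then an increase of D + A + R whenever that sum is positive, but the endpoint shows none.
2. If D + A + R is greater than k × U, the net result is an increase while S still shows a saving of k × U.
3. D does not appear in S, so S cannot give the footprint named in 3.0.
4. S overstates the net saving if D + A + R is above zero and understates it if the sum is below zero. D and A are additions. R may be negative, because 5.2 expects fewer clinic visits. The sign of the sum is therefore open.

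**Inputs available.** The Protocol gives no value for k, U, D, A or R. The sign and size of the gap between S and the net saving cannot be calculated from it.

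**The case against.** The strongest reply is that the endpoint does answer the carbon question as most of the Protocol puts it. Sections 6.0 and 6.2 ask about carbon avoided by preventing ulcers, which is a legitimate quantity. On this view the Study Summary line is loosely worded and could simply be corrected. A one-line endpoint also need not set system boundaries or emission factors, which a modelling plan could supply.

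Much of this stands. It would be wrong to say that the endpoint fails the Protocol's carbon aims in general; it fails the one in 3.0. The lack of model detail is no finding either. What remains is that the quantity, its rank and its breakdown by geography differ between sections. These belong in the Protocol, and a later plan should not have to choose among them. Correcting 3.0 alone would leave the rank unresolved and would leave no measure able to show a net increase.

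Two stronger readings are tempting, and the document supports neither.

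- **That the result is biased towards the device.** Leaving out device emissions and alert visits would flatter the device, but leaving out any saved routine travel would work against it. The balance is unknown.
- **That the omission can be sized from the Protocol's own figures.** A reader might start from the 40% first-year recurrence in 5.1. That rate applies after a previous ulcer, whereas 8.1 requires only high-risk status and intact feet. The allocation ratio, the treatment effect and the alert rate are not stated. Because the device is retained at Day 84, charging its whole footprint to 12 weeks of use would also be unjustified when its service life is not given.

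**Conclusion.** The point holds as one of inconsistent definition with a one-sided endpoint. The Protocol names two carbon quantities at two ranks. The version listed as primary covers only avoided ulcer care, so it cannot deliver the footprint of Path Active and cannot show a net increase. This rests on the wording alone and needs no numerical assumption. The size and direction of any net bias are indeterminate from the document, and no figure should be attached to them. The change is worth making because it decides what the trial may claim about carbon.

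**What to change.** Use one definition at one rank in 3.0, 6.2 and 15.1.1. Make it secondary, as both aims already are. The endpoint would be the signed between-arm difference in modelled carbon per randomised participant, reported by geography with its uncertainty. It would cover:

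- device and app emissions, spread over the device's service life;
- foot-clinic travel, both routine and alert-triggered;
- ulcer treatment.

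Feed it with ulcers and visits observed in both arms, not with an assumed number prevented. This matters because the only ulcer item among the endpoints (15.1.2) is tied to a review of Path Active alerts, which arise only in the device arm. Carbon avoided through ulcer prevention can stay as a separately labelled component, which still answers 6.0.

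The costs are modest but real:

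- The schedule in 10.2 has no line for routine podiatry visits, travel distance or mode, so visit counts must be extracted for both arms. It has no separate line for new ulcers either, so the forms should be checked to confirm that they capture them in both arms.
- Travel inputs that are not recorded, and emission factors, must be stated as assumptions with a range.
- With few ulcers expected over 84 days, the estimate will be imprecise.
- The reported saving may be smaller, or negative.
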